#### 6.2. NEUROLOGICAL SYMPTOMS

Next, we present the frequency distributions of neurological symptoms for Cohort 2 according to the three temporal moments: baseline, assessment 1, and assessment 2.

## 6.2.1. Overall Neurological Symptoms: Comparison between Baseline and First Two Assessments

Table 146: Comparison of Neurological Symptoms

Headache No Yes  Epilepsy No Yes  Motor deficit No Yes  Sensory deficit No Yes  Sensory deficit No Yes  Speech deficit No Yes  Speech deficit No Yes  Pres  Pres  No Yes  Pres  Presence of at least one symptom No Yes  Number of neurological symptoms  1 2 3 4	
Feilepsy No No Yes  Motor deficit No Yes  Sensory deficit No Yes  Spech deficit No Yes  Others No Yes  Others No Yes  Presence of at least one symptom No Yes  Number of neurological symptoms  1 2 3 4	Headache
No   Yes	No
No   Yes	Yes
No   Yes	Epilepsy
Motor deficit No Yes Sensory deficit No Yes Spech deficit No Yes Others No Yes Others No Yes Presence of at least one symptom No Yes Number of neurological symptoms  1 2 3 4	
No Yes  Sensory deficit  No Yes  Speech deficit  No Yes  Others  No Yes  Presence of at least one symptom  No Yes  Number of neurological symptoms  1 2 3 4	Yes
No Yes  Sensory deficit  No Yes  Speech deficit  No Yes  Others  No Yes  Presence of at least one symptom  No Yes  Number of neurological symptoms  1 2 3 4	Motor deficit
Sensory deficit No Yes Speech deficit No Yes Others No Yes Presence of at least one symptom No Yes Number of neurological symptoms  1 2 3 4	
No Yes  Speech deficit No Yes  Others No Yes  Presence of at least one symptom No Yes  Number of neurological symptoms  1 2 3 4	Yes
Yes  Speech deficit  No Yes  Others  No Yes  Presence of at least one symptom  No Yes  Number of neurological symptoms  1 2 3 4	Sensory deficit
No Yes Others No Yes Presence of at least one symptom No Yes Number of neurological symptoms  1 2 3 4	No
No Yes Others No Yes Presence of at least one symptom No Yes Number of neurological symptoms  1 2 3 4	Yes
Yes Others No Yes Presence of at least one symptom No Yes  Number of neurological symptoms  1 2 3 4	Speech deficit
Others No Yes  Presence of at least one symptom No Yes  Number of neurological symptoms  1 2 3 4	No
No Yes  Presence of at least one symptom  No Yes  Number of neurological symptoms  1 2 3 4	Yes
Yes Presence of at least one symptom No Yes Number of neurological symptoms 1 2 3 4	Others
Presence of at least one symptom  No  Yes  Number of neurological symptoms  1 2 3 4	
one symptom  No Yes  Number of neurological symptoms  1 2 3 4	
No Yes Number of neurological symptoms  1 2 3 4	Presence of at least
Yes Number of neurological symptoms  1 2 3 4	
Number of neurological symptoms  1 2 3 4	
neurological symptoms  1 2 3 4	
1   2   3   4	
1 2 3 4	neurological
2 3 4	
3 4	·
4	
1 Me remort form in values for each variable compared by complete. The first in value	0

1. We report four p-values for each variable, separated by semicolons. The first p-value represents the comparison of the differences between the three assessments. Subsequent p-values correspond to pairwise comparisons: Baseline vs. Assessment 1, Baseline vs. Assessment 3, and Assessment 2 vs. Assessment 3. For dichotomous variables,

Cochran's Q test and McNeiman's test were used. The discrete variable 'number of symptoms' was analyzed with the Friedman and Wilcoxon tests, respectively.

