## Methodology:

This is a phase II clinical trial, with two cohorts of patients included in parallel, all with melanoma BRAF mutated and brain metastases without previous local treatment in the brain. Cohort 1 will include patients with asymptomatic brain metastases and cohort 2 will include patients with symptomatic brain metastasis.

BRAF mutation status will be tested locally using a validated test before patient inclusion, patients will receive both encorafenib 450 mg/day and binimetinib 45 mg/12 h (twice a day) (COMBO450) until progression disease (PD), toxicity or death. After 56 days of treatment, a contrast enhanced brain MRI and body CT scan will be performed as the first tumour assessment. Depending on the outcome of this image test, patients undergo local radiation treatment (radiosurgery or whole brain radiotherapy (WBRT) as per local radiotherapy oncologist. Encorafenib and binimetinib will be interrupted 24h before radiotherapy and restart 24h after the last dose of radiotherapy. After local treatment encorafenib and binimetinib will be administered at same doses until PD, toxicity or death. After progression, patients will be followed only for overall survival. In the case of COMBO450 is providing a clinical benefit to any patient, treatment could be continued, after agreement with Sponsor.

This study will be carried out following good clinical practices (GCP) guidelines as per European and Spanish regulations for clinical investigations.

Number of patients (planned): At least 63 patients.

Cohort 1: N=48; Cohort 2: N=15.

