#### Statistical methods:

The sample calculation has been done for the **primary endpoint (cohort 1)** and it's based on a Fleming's Single Stage Procedure:

We want to show that the Intracranial response rate by modified RECIST 1.1 before local treatment is superior or equal to the reference value, say, 90=40%. Under the hypothesis to have a response rate under new treatment ( $\pi$ 1) of 60% with  $\alpha$  risk = 5% in one-sided test and a power of 80%, the required sample size is 38 patients.

Finally, if 20% of patients will be lost of follow up, die or progress before day 56 without doing the first tumour assessment (according data published in COMBI-MB study), the initial sample size will be 48 patients, to obtain 38 evaluable patients.

Data of study will be analysed in the following populations:

- ITT: All patients that has been enrolled in the trial
- Evaluable population (PP): All patients fulfilling all eligibility criteria and having at least two valid tumour assessments (baseline and one evaluation MRI or CT-scan) without any protocol deviation that makes the patient invalid for the primary endpoint evaluation.
- Safety population: All patients receiving at least one dose of treatment.

Cohort 2 (N=15) is exploratory and no formal sample calculation has been performed, a descriptive analysis will be performed on the same variables and population as cohort 1 (N=48). The only difference is that the population included will be symptomatic. The efficacy and safety as an overall of both cohorts in conjunction will be also addressed.				

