## 5.3. Patient Inclusion and Cohort Assignment

During the screening (28 days before day 1 cycle 1) it should be assessed whether the patient is symptomatic (cohort 2) or asymptomatic (cohort 1).

Definition of Asymptomatic (cohort 1):.Patients without active symptoms secondary to brain metastases at the moment of inclusion.

After confirming that a patient fulfils all eligibility criteria of the study (inclusion/exclusion criteria), site staff will initiate the eCRF registration procedure.

Once procedure is fulfilled the site staff will receive the "Inclusion confirmation communication", and protocol-specific treatment can be initiated.

This is an open label, single arm study including two cohorts of patients, in each cohort, patients will be treated with encorafenib 450 mg once daily and binimetinib 45 mg twice daily.

After 56 days of treatment, a contrast enhanced brain MRI and CT body scan will be performed as first tumour assessment:

- Patients with PD at first evaluation in brain MRI (modified RECIST 1.1 criteria) and /or body CT scan (RECIST 1.1 criteria) will discontinue study treatment and will continue in the study for OS follow-up.
- Patients with CR in brain (modified RECIST 1.1) and no PD in the body (RECIST 1.1), will continue study treatment and will be followed every two months with contrast enhanced brain MRI and body CT scan up to 12 months. If no PD after one year, patients will be followed as per institutional criteria, and continue with the treatment.
  - o If considered by the investigator, local treatment can be done for brain CR patients, but only after confirming no safety concerns (defined as substantial deterioration of vital signs (including ECOG PS), physical examination, ECG, Lab. Values that do not recommend RT) with the three first patients treated with radiation therapy in the running phase (for more information, please see section 9.1).
- Patients with no CR and no PD in brain MRI per modified RECIST 1.1 criteria, and no PD in body per RECIST 1.1 criteria, will be treated with local RT and/or radiosurgery, and then will continue Enco and Bini. The first 3 patients will be treated in a running

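### SAP 6.2.1 tests the any-symptom variable against baseline in a cohort selected for having symptoms, so change can essentially only be improvement, and two of its three named pairs do not match the defined times

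*Combined protocol and SAP*

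**What the plan says.** SAP 6.2 presents neurological symptoms in cohort 2 "according to the three temporal moments: baseline, assessment 1, and assessment 2". Table 146 (SAP 6.2.1) has eight variables: headache, epilepsy, motor deficit, sensory deficit, speech deficit, others, a yes/no row for "Presence of at least one symptom", and the number of symptoms.

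The table footnote promises four p-values per variable. The first compares all three times (Cochran's Q for yes/no variables, Friedman for the count). The other three are pairwise (McNemar or Wilcoxon): "Subsequent p-values correspond to pairwise comparisons: Baseline vs. Assessment 1, Baseline vs. Assessment 3, and Assessment 2 vs. Assessment 3". The SAP does not say whether tests are exact or asymptotic, what significance level applies, or which patients enter each comparison.

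On who is in the cohort, the protocol synopsis (Methodology) says "cohort 2 will include patients with symptomatic brain metastasis". Protocol 5.3 describes cohort 1 as "Patients without active symptoms secondary to brain metastases at the moment of inclusion", so cohort 2 takes those with active symptoms. On the status of the analysis, the synopsis (Statistical methods) says: "Cohort 2 (N=15) is exploratory and no formal sample calculation has been performed, a descriptive analysis will be performed". Protocol 10.7 adds that analyses use observed data and that values missing after dropout are not replaced.

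**The concern.** McNemar's test asks whether changes in one direction are as frequent as changes in the other. That is informative only if patients can move both ways. Here the any-symptom row is at its ceiling at baseline because of how the cohort was chosen, and the table's category for other symptoms catches any complaint not listed. A patient who gets worse stays at yes. A patient whose symptoms fluctuate, or settle on the steroids that protocol 6.1 permits, moves to no and counts as an improvement. With no control group, nothing separates these from a drug effect.

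Two further points affect how the table can be read. Cochran's Q and Friedman need all three readings, so patients without them leave those tests and any percentage based on the same set. And two of the three named pairs use an Assessment 3 that SAP 6.2 does not define, so a reader cannot be sure which comparison lies behind those p-values. At stake is an exploratory statement about symptom relief in symptomatic patients.

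**Working it through.** **Inputs.** From the documents: 15 planned cohort 2 patients (synopsis); three times (SAP 6.2); the named tests (Table 146 footnote). SAP 6.2 states no sample size, power or alpha, so it has no figure to reproduce. Assumed here: a two-sided 0.05 threshold; every patient is yes at baseline; and a share q of patients symptom-free at follow-up for reasons other than the drug, taken over a range.

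**How many symptom-free patients give p<0.05.** Let b be the number going from yes to no between baseline and a later time. No patient can go from no to yes.

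- Exact McNemar, p = 2 × 0.5^b: b=5 gives 0.0625; b=6 gives 0.031.
- McNemar, uncorrected, chi-square = b on 1 df: b=3 gives 0.083; b=4 gives 0.046.
- McNemar, continuity-corrected, chi-square = (b−1)²/b: b=5 gives 0.074; b=6 gives 0.041.
- Cochran's Q with k patients clear at both later times, Q = 2k on 2 df: k=2 gives 0.135; k=3 gives Q=6, p=0.0498. The exact permutation value for k=3 is 3/3³ = 0.111, and for k=4 it is 3/3⁴ = 0.037.

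So the threshold is 3, 4 or 6 patients, depending on a choice the SAP leaves open. If nobody clears, p=1.

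**Chance of p<0.05 with no drug effect, n=15** (binomial tail at each threshold):

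| q | Exact McNemar (6 or more) | Uncorrected McNemar (4 or more) | Asymptotic Q, same patients clear twice (3 or more) |
|---|---|---|---|
| 0.1 | 0.002 | 0.06 | 0.18 |
| 0.2 | 0.06 | 0.35 | 0.60 |
| 0.3 | 0.28 | 0.70 | 0.87 |
| 0.4 | 0.60 | 0.91 | 0.97 |
| 0.5 | 0.85 | 0.98 | 1.00 |

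**Loss of patients.** The documents give no loss rate for cohort 2. Borrowing the 20% that protocol 10.1 assumes for cohort 1 would leave 15 × 0.8 = 12. If the loss is random, the chances fall: at q=0.3 and n=12, exact McNemar gives 0.12 and asymptotic Q 0.75. If only still-symptomatic patients are lost, the symptom-free share among those remaining rises: 0.30/0.80 = 0.375. Patients who are yes throughout add nothing to either statistic, so that kind of loss inflates the percentage while leaving the p-value as it was. The exact p is 0.031 for 6 of 15 (40%) and for 6 of 12 (50%) alike, so the p-value hides the denominator.

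**Pair labels.** Three times give three pairs: baseline–1, baseline–2 and 1–2. The footnote names baseline–1, baseline–3 and 2–3. If baseline is counted as assessment 1, the last two become baseline–2 and 1–2, but the first then compares baseline with itself. Neither numbering makes all three labels right.

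**What replaces the test.** Exact (Clopper-Pearson) 95% CIs out of 15: 3/15 = 20% (4.3% to 48.1%); 6/15 = 40% (16.3% to 67.7%).

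**The case against.** The best defence is that this is a small matter. Neurological symptom change is not among the protocol's objectives or endpoints, the table sits under the SAP's other analyses, and cohort 2 is openly exploratory. That stands, and it limits the weight of the point.

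It is also fair that the ceiling fully affects only one of eight variables. The six single-symptom rows can move either way. The count is at least 1 at entry but can rise. Even the any-symptom row may contain a few no values, because protocol 5.3 allows cohort assignment up to 28 days before day 1. The assessment 1 versus assessment 2 comparison of that row is free of the ceiling.

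On losses, the pairwise tests need two readings, not three. A patient progressing at the first evaluation still has the week 8 neurological examination (protocol 8.2) and can enter baseline versus assessment 1. The complete-case restriction follows from Cochran's Q and Friedman; SAP 6.2 does not state it as a rule. The pair labels look like a numbering slip.

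A reader might go further and infer that a significant improvement is all but guaranteed. The table above does not support this: the chance runs from under 1% to nearly 100%, and the high end needs asymptotic tests together with a symptom-free share that the documents do not give. A reader might also infer that a particular number of the 15 will be left in the tests, or that symptom relief is a leading claim of the trial. The documents give no loss figure for cohort 2 and build no claim on these p-values.

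**Conclusion.** The point holds in a limited form. For the any-symptom row, tests that include baseline can essentially record only improvement, because patients were selected on the baseline value. Their p-values therefore do not separate benefit from fluctuation or steroid effect, and the threshold shifts between 3, 4 and 6 symptom-free patients according to an unstated choice of test. Selective loss can also inflate the symptom-free percentage among completers, by an amount the documents do not allow one to state. Two of the three pair labels need correction.

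This rests on essentially all cohort 2 patients having a recorded symptom at baseline, and on a 0.05 threshold that SAP 6.2 does not give. It does not show that significance is built in, that the other seven variables are invalid, or that any primary or secondary objective is affected.

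**What to change.** In SAP 6.2.1:

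- Remove the any-symptom p-values that involve baseline (Cochran's Q and the McNemar tests against baseline).
- Report instead, out of all cohort 2 ITT patients, the number symptom-free at assessment 1 and at assessment 2, each with an exact 95% CI. Show those who died, progressed or were not assessed as separate lines.
- Keep the single-symptom rows and the symptom count descriptive. If they are tested, use exact tests, give the number of patients in each comparison, and note that the count is at least 1 at entry.
- Relabel the pairs as baseline versus assessment 1, baseline versus assessment 2, and assessment 1 versus assessment 2.

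The cost is a footnote correction, one re-programmed table and the loss of some exploratory p-values. No new data are needed.

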## 7. OTHER ANALYSES REQUIRED BY THE COORDINATOR

Group A: Symptomatic patients (Those belonging tp symptomatic cohort 2).

Group B: Asymptomatic patients, both those who were not treated with corticosteroids or anticonvulsants and those who were treated without association with brain metastases.

Group C: Patients who were asymptomatic at the time of study treatment but had been treated with corticosteroids in the days before due to a symptom of the disease.

#### 7.1. INTRACRANIAL OVERALL SURVIVAL (IOS).

7.1.1. SYMPTOMATIC PATIENTS A+C: INTRACRANIAL OVERALL SURVIVAL (IOS).

Table 147: Events type OS

os	
Alive	
Death	
Total	

Table 148: Median/mean OS (estimated by Kaplan-Meier)

	Median (months)	CI 95%	Mean	CI 95%
Overall survival				

Table 149: OS estimated survival ratio

os	Events (%, total N)	Patients at risk	% estimated cumulative survival ratio	CI 95%
At 6 months				
At 12				
months				
At 18				
months				
At 24				
months				

Figure 18: Overall survival

## 7.1.2. ASYMPTOMATIC PATIENTS B: INTRACRANIAL OVERALL SURVIVAL (IOS).

Table 150: Events type OS

os	N	%	95%CI
Alive			
Death			
Total			

Table 151: Median/mean OS (estimated by Kaplan-Meier)

	Median (months)	CI 95%	Mean	CI 95%
Overall survival				

Table 152: OS estimated survival ratio

os	Events (%, total N)	Patients at risk	% estimated cumulative survival ratio	CI 95%
At 6 months At 12 months At 18 months At 24 months				

Figure 19: Overall survival

#### 7.1.3. INTRACRANIAL OVERALL SURVIVAL (IOS) VS SYMPTOMATIC.

Table 153: Events type OS

Symptomatic group		
Death		
Alive		

1. Pearson's Chi-squared test

Table 154: Median/mean OS (estimated by Kaplan-Meier)

	Median (months)	CI 95%	Mean	CI 95%
No				
Yes				

Table 155: OS estimated survival ratio

os	Events (%, total N)	Patients at risk	% estimated cumulative survival ratio	CI 95%
No				
At 6 months				
At 12				
months				
At 18				
months				
At 24				
months				
Yes				
At 6 months				
At 12				
months				
At 18				
months				
At 24				
months				

Figure 20: Overall survival vs Symptomatic group

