# 8.3. Study timetable and end of study

- Expected recruitment period: 36 months
- Expected follow-up: 24 months

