performed within 6 months after database closure expected at 24 months after last patient inclusion, however interim analysis might be performed when analysing other primary variables

Percentage of patients (%) free of extracraneal progression at 6 (week 24), 12 (week 28) and 24 months (week 96): percentage of patients free of progression by RECIST 1.1 at 6 months (week 24), 12 months (week 48) and 24-month (week 96) considering date of inclusion. The final statistical analysis of this endpoint is expected to be performed within 6 months after database closure expected at 24 months after last patient inclusion, however interim analysis might be performed when analysing other primary variables.

**Overall Survival in both cohorts (OS):** OS is calculated as the time from date of inclusion to date of death due to any cause. The final statistical analysis of this endpoint is expected to be performed within 6 months after database closure expected at 24 months after last patient inclusion, however interim analysis might be performed when analysing other primary variables.

Percentage of patients (%) alive at 6, 12 and 24 months in both cohorts: percentage of patients alive at 6 months, 12 month and 24-month considering date of inclusion. The final statistical analysis of this endpoint is expected to be performed within 6 months after database closure expected at 24 months after last patient inclusion, however interim analysis might be performed when analysing other primary variables.

**Toxicity of the combination until local treatment:** Number of patients with adverse events and serious adverse events, changes in laboratory values, vital signs, electrocardiograms (ECGs), LVEF (MUGA (Multigated Acquisition Scan) / echocardiogram) and assessment of physician, dermatological and ocular examinations graded according to the National Cancer Institute (NCI) Common Terminology Criteria for Adverse Events (CTCAE) v 4.03 until local treatment (local treatment D1). It will be studied using descriptive statistics techniques, such as frequency tables and contingency tables. The final statistical analysis of this endpoint is expected to be performed within 6 months after database closure expected at 24 months after last patient inclusion, however interim analysis might be performed when analysing other primary variables.

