#### 10.6. Statistical analysis

For each categorical variable, the results will be summarized by frequencies and percentages. For each continuous variable, the results will be summarized by descriptive statistics such as median, range, and interquartile range or by means, standard deviations and 95% confidence intervals (CIs). For proportions, point estimates and exact 95% confidence intervals will be calculated. For time to event endpoints, Kaplan-Meier estimates at selected time points and corresponding curves will be presented. Time to event is derived relative to the first study treatment administration. Laboratory values will be expressed as the absolute values and as grading (ordinal categorical variables) according to NCI CTCAE v 4.03.

Treatment-emergent AE (AEs starting after the administration of study treatment and up to study completion) will be summarized by system organ class and preferred term. Grading will be presented by type and grade in tables showing frequency and percentage of the within-patient worst grades. In addition, grade ≥3 AEs will be summarized separately. Full analysis details will be outlined in the statistical analysis plan (SAP).

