# 3.5. TREATMENT COMPLIANCE

Upon database closure, there are 4 patients still undergoing treatment.

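### The exploratory group comparisons of OS, iPFS and ePFS name only a Pearson chi-squared test on status counts, which ignores event times and has much less power than a log-rank test

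*Combined protocol and SAP*

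**What the plan says.** SAP 7.1.3 (Table 153) cross-tabulates death/alive by symptomatic group, with the footnote "Pearson's Chi-squared test". The same footnote stands under:

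- SAP 7.2.3, Table 162 (iPFS, event or censored);
- SAP addendum 2.4, Table 12 (ePFS, with an explicit p-value column);
- SAP addendum 2.2 and 2.3, Tables 6 and 9 (OS and iPFS by radiotherapy).

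Each of these sections also has a Kaplan-Meier median/mean table by group (Table 154 is titled "Median/mean OS (estimated by Kaplan-Meier"), survival at fixed times with confidence intervals and numbers at risk, and a curve. None of these carries a named test.

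Protocol 10.6 is descriptive: "For time to event endpoints, Kaplan-Meier estimates at selected time points and corresponding curves will be presented". Neither document names a log-rank test, a Cox model or a hazard ratio.

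The groups are defined in SAP section 7. A is cohort 2. C is taken from the asymptomatic patients: "Patients who were asymptomatic at the time of study treatment but had been treated with corticosteroids in the days before", because of a disease symptom. B is the rest. The size of C is not given.

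**The concern.** OS, iPFS and ePFS are times to an event with censoring. A chi-squared test on final status treats a death at month 2 and a death at month 40 as the same outcome. It also treats a patient censored at month 4 and one event-free at month 50 as the same.

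Two things can follow. If most patients have had the event by database closure, the counts look alike even when one group fails much sooner, so a real difference is missed and a non-significant p-value may be read as no difference by symptoms. If one group has been followed much longer, its extra events can look like a difference that is not there. The first follows from the plan's own timetable. The second needs a condition that the documents do not establish.

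**Working it through.** **The plan's own calculation.** The only design figure is for response: n = [(1.645·√(0.4·0.6) + 0.842·√(0.6·0.4))/0.2]² = 37.1, so 38, and 38/0.8 = 47.5, so 48. This reproduces the protocol. No size or power is stated for any survival comparison.

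**Inputs from the documents.** Size: "Cohort 1: N=48; Cohort 2: N=15", 63 in all. Accrual: "Expected recruitment period: 36 months". Closure: "database closure expected at 24 months after last patient inclusion". Potential follow-up is therefore about 24 to 24 + 36 = 60 months. Protocol 2.3 gives a median OS of about 9 months with treatment. Protocol section 3 gives a median PFS of 5.6 months in the main cohort of the dabrafenib-trametinib brain-metastasis trial.

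**Assumptions.** Hazard ratio 2; exponential survival; A+C of 15, 25 or 31; the medians above placed in the symptomatic group, so 9 vs 18 months (OS) and 5.6 vs 11.2 (iPFS). A second OS pair, 6 vs 12, is purely assumed.

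**Expected share with the event.** With λ = ln 2/median and follow-up uniform on 24-60 months, the share is 1 − [e^(−24λ) − e^(−60λ)]/(36λ). OS: 94.7% (median 9) vs 78.5% (median 18). iPFS: 98.9% (5.6) vs 90.9% (11.2).

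**Check by hand, iPFS, A+C = 15.** Expected event-free patients are 15 × 0.011 = 0.2 and 48 × 0.091 = 4.4. With none of 15 and k of 48 event-free, chi-squared = 63·(15k)²/[15·48·k·(63 − k)] = 19.69k/(63 − k). At k = 4 this is 1.33. At k = 10 it is 3.71 and at k = 11 it is 4.16, so 11 event-free patients in B are needed to pass 3.84, where about 4 are expected. A doubling of median iPFS is almost undetectable.

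**Simulated power** (10,000 trials per scenario, two-sided 5%, no continuity correction), chi-squared / log-rank:

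| A+C of 63 | OS 9 vs 18 | OS 6 vs 12 | iPFS 5.6 vs 11.2 |
|---|---|---|---|
| *Follow-up 24-60 months* | | | |
| 15 | 21% / 62% | 0.8% / 64% | 0.3% / 64% |
| 25 | 41% / 71% | 14% / 74% | 9% / 75% |
| 31 | 53% / 72% | 31% / 75% | 25% / 75% |
| *Follow-up fixed at 24 months* | | | |
| 15 | 41% / 56% | 31% / 62% | 26% / 62% |
| 25 | 56% / 64% | 51% / 70% | 49% / 72% |
| 31 | 58% / 65% | 59% / 71% | 58% / 72% |

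ePFS was not simulated, since the documents give no median for it.

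**Type I error with no true difference.** With the same follow-up in both groups, chi-squared rejects in 0.1-5.5% of trials and log-rank in 5-6%. With entry shifted by 6 months between groups, chi-squared reaches at most about 9%. With entry periods fully separated (A+C followed 42-60 months, B 24-42) and a median OS of 18 months, chi-squared rejects in 16%, 27% and 30% for A+C of 15, 25 and 31; log-rank stays at 5-6%. Under the same separation, iPFS with a median of 5.6 months shows no inflation (0-0.3%), because hardly anyone remains event-free.

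**Kaplan-Meier mean.** No truncation time is stated. For one exponential curve with median 12 months (m = 12/ln 2 = 17.3), the mean restricted at t is m(1 − e^(−t/m)): 13.0 months at t = 24 and 16.7 at t = 57.

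**The case against.** The strongest reply is that little rests on these p-values. The tables are coordinator-requested extras, A+C versus B is in no protocol objective, cohort 2 is descriptive, and the trial is judged on intracranial response. Time is also not ignored in these sections as a whole, since Kaplan-Meier estimates and curves by group sit beside the counts. The figures are missing from the available text, so a log-rank p-value printed on a curve cannot be excluded, although none is specified. All of this stands, and it limits the severity. It does not make the one named test suitable.

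The size of the power loss depends on assumptions. Protocol 8.1 describes survival contact up to 24 months or study closure. With follow-up fixed at 24 months, the OS gap narrows to about 7-31 points. That also stands.

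Three stronger readings are tempting and not supported:

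- *That the test will create false differences.* This needs strongly different follow-up. The synopsis says that the two cohorts are recruited in parallel, and nothing shows that A+C and B entered at different times.
- *That these are the planned comparisons of the second publication.* The publication policy mentions possible comparisons between the two cohorts, and A+C versus B is a different grouping. The by-cohort survival sections (SAP 4.5-4.7) name no test.
- *That the group means are not comparable.* No document says where the curves are cut. The gap between 13.0 and 16.7 months needs very different last observation times. What is shown is only an unstated truncation time.

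**Conclusion.** The point holds as an unsuitable choice of test in exploratory tables. For censored endpoints, the only named inference uses final status alone. At a hazard ratio of 2 and follow-up of 24-60 months, power is about 1-53% against 62-75% for OS and 0-25% against 64-75% for iPFS. The hazard ratio, the exponential shape, the size of A+C and the second OS pair of medians are assumptions, which is why ranges are given. Type I error is near or below nominal when follow-up is similar, so false positives are a conditional risk and not a demonstrated one. The primary endpoint and the trial's success criterion are untouched. Severity is minor to moderate.

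**What to change.** - In SAP 7.1.3, 7.2.3 and addendum 2.4, replace the chi-squared test by a log-rank test and a Cox hazard ratio with 95% CI, labelled exploratory. Keep the event counts as description, without a p-value.
- In addendum 2.2 and 2.3, remove the chi-squared p-value. A plain log-rank test is not the remedy there: radiotherapy follows the day-56 assessment, so patients must survive to receive it, and a simple yes/no comparison carries immortal-time bias.
- If a Kaplan-Meier mean is reported by group, state one common truncation time (for example 24 months), or drop the mean.

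The cost is a few lines of SAP text and code. No new data are needed.
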